8.1.1. Calculation of the Summary Statistics

For continuous data the following rules will be applied:

- Missing values will not be imputed, unless specifically stated otherwise.
- Unrounded data will be used in the calculation of summary statistics.
- If the number of subjects with valid observations (n) <3, summary statistics will not be calculated, with the exception of n, minimum, and maximum.
- As Early Termination measurements are not associated with any scheduled timepoint, it will be excluded from all calculations of summary statistics.
- Post dose repeats and unscheduled assessments will not be included in calculation of summary statistics.

For categorical data the following rules will be applied:

- If the categories of a parameter are ordered (eg, AE severity), all categories between the possible minimum and maximum categories will be included, even if n = 0 for a given category. If the categories are not ordered (eg, race), only those categories for which there is at least 1 subject represented will be included.

- Missing values will not be imputed, with the exception of AEs where the ‘worst-case’ approach will be taken (see [Section 8.6.1](#)), or unless specifically stated otherwise. A ‘missing’ category will be included for any parameter for which information is missing. This will ensure that the population size totals are consistent across different parameters.

8.1.2. Repeat and Unscheduled Readings

For vital signs and ECG data only, any predose value recorded in addition to the original value or a postdose value recorded within 15 minutes of the original value will be defined as a repeat value; any postdose value recorded more than 15 minutes after the original value will be defined as an unscheduled value. For all other data types (eg, laboratory parameters), any value recorded in addition to the original value will be defined as an unscheduled value.

The original scheduled value will be used in all calculations post dose. In the event of any repeats or unscheduled measurements taken pre-dose the values will be considered when determining the baseline value for each period.

Post dose repeats, unscheduled assessments, and ET measurements will be excluded from all calculations, with the exception of the baseline derivation (see [Section 8.1.3](#)).

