| | | | | | | | | | | | | | S | tudy | v Daj | ys | | | | | | | | | | | Clinic Discharge/ EOT (Day 25) or ET ^v | Follow -up Phone Call (EOS) |
|--|----------------------------------|---|---|---|---|---|---|---|---|---|---|----|----|------|-------|----|----|----|----|----|----|----|----|----|----|----|---|---|
| Study Procedures ^a | Screening (Days -29 to -2) | | | 2 | 3 | 4 | 5 | 6 | 7 | 8 | 9 | 10 | 11 | 12 | 13 | 14 | 15 | 16 | 17 | 18 | 19 | 20 | 21 | 22 | 23 | 24 | | 7 (±2) days post EOT or ET ^w |
| Prior and Concomitant Medications ^s | X | Х | Х | X | Х | X | X | X | Х | Х | Х | X | Х | X | Х | X | X | X | X | X | X | Х | X | X | X | X | Х | Х |
| Serum Pregnancy Test ^t | Х | Х | | | | | | | | | | | | | | | | | | | | | | | | | Х | |
| FSH Test ^u TSH Test | X X | | | | | | | | | | | | | | | | | | | | | | | | | | | |

Abbreviations: AE = adverse event; BMI = body mass index; BP = blood pressure; CBC = complete blood count; CK = creatine kinase; CRU = Clinical Research Unit;

ECG = electrocardiogram; EOS = End of Study; EOT = End of Treatment; ET = Early Termination; FSH = follicle-stimulating hormone; HbA1c = hemoglobin A1c; HDYF? = How Do You Feel?; HIV = human immunodeficiency virus; ICF = Informed Consent Form; PK = pharmacokinetic; SAE = serious adverse event; TSH = thyroid-stimulating hormone; UA = urinalysis.a. For details on study procedures, see Section 7.

b. Interim medical history only.

c. Weight and BMI (based on Screening height) only.

d. A complete physical examination will be performed at Screening. An abbreviated physical examination will be performed at Check-in (Day -1) and at EOT (Day 25).

- e. 12-lead ECGs will be collected after the subject has rested in the supine position for at least 10 minutes, and will be obtained prior to and as close as possible to the scheduled blood draws at Screening and Day -1, Day 1 (predose and 2 hours after LOXO-305 dosing), Day 4 (ie, 72 hours after LOXO-305 dosing on Day 1), Day 8 (predose), Day 11 (ie, 72 hours after LOXO-305 dosing on Day 8), Day 15 (predose), Day 18 (predose), Day 21 (ie, 72 hours after LOXO-305 dosing on Day 18), and at EOT/Day 25 (168 hours after LOXO-305 dosing on Day 18) or ET.

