
- j. On Day 1, LOXO-305 will be administered in the morning, either following a fast of at least 10 hours prior to and 4 hours after the LOXO-305 dose or approximately 30 minutes after the start of a standard breakfast, according to the treatment sequence the subject is randomly assigned to. Standard breakfast should be entirely consumed within 30 minutes.
- k. On Day 8, LOXO-305 will be administered in the morning, either following a fast of at least 10 hours prior to and 4 hours after the LOXO-305 dose or approximately 30 minutes after the start of a standard breakfast, according to the treatment sequence the subject is randomly assigned to. Standard breakfast should be entirely consumed within 30 minutes.
- 1. On Days 15, 16, and 17 omeprazole will be administered in the morning following a fast of at least 8 hours prior to the omeprazole dose, followed by a standard breakfast administered approximately 1 hour after dosing. Standard breakfast should be entirely consumed within 30 minutes.
- m. On Day 18, LOXO-305 and omeprazole will be co-administered in the morning, following a fast of at least 10 hours prior to and 4 hours after the omeprazole and LOXO-305 coadministration.

CCI

- p. Clinical chemistry panel including CK (fasted at least 8 hours), coagulation parameters, CBC, and UA will be performed at Screening, Check-in (Day -1), Days 4, 7, 11, 17, 21, and at EOT (Day 25) or ET.
- q. Hemoglobin A1c test performed at Screening only.
- r. Alcohol breath test and drugs of abuse urine test, including cotinine. Results from the alcohol and drug tests will be used to determine subject eligibility per the inclusion/exclusion criteria.
- s. Prior and concomitant medication administration will be recorded beginning at informed consent. In addition, all Investigator-approved medications taken by a subject within 30 days prior to study drug administration for non-prescription medications, will be recorded on the subject's electronic Case Report Form.
- t. Female subjects only.
- u. Post-menopausal female subjects only.

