8. STATISTICAL METHODOLOGY

8.1. General

Listings will be provided for all data captured in the database. Listings will include all subjects assigned to the all subjects population and include data up to the point of study completion or discontinuation. Subjects are generally considered to have completed the study if they completed all protocol-specified procedures and assessments for the end-of-treatment visit. Any subject who discontinued the study will be identified accordingly in the listings. Summaries and statistical analyses will include the subjects assigned to the relevant population based on data type.

Data analysis will be performed using the SAS® statistical software package Version 9.4 (or higher if upversioned during the study).

Analysis Data Model (ADaM) datasets will be prepared using Clinical Data Interchange Standards Consortium (CDISC) ADaM Version 2.1 (or higher if upversioned during the study) and CDISC ADaM Implementation Guide Version 1.2 (or higher if upversioned during the study). Pinnacle 21 Community Validator Version 2.2.0 (or higher if upversioned during the study) will be utilized to ensure compliance with CDISC standards.

Caution should be used when interpreting results from the statistical analyses conducted in this study because the sample size is not based on power calculations.

Where reference is made to 'all calculations', this includes, but is not limited to, summary statistics, statistical analyses, baseline derivation, and changes from baseline.

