8.6.3. Vital Signs Parameters

All vital signs parameters with changes from baseline will be listed; any value outside the clinical reference range will be flagged, and whether the out of range value was deemed clinically significant or not clinically significant will be indicated.

The observed results and change from baseline for all vital signs parameters will be summarized descriptively by treatment group and timepoint. Boxplots of the observed values will also be provided.

8.6.4. 12-lead Electrocardiogram Parameters

All 12-lead ECG parameters with changes from baseline will be listed; any value outside the clinical reference range will be flagged, and whether the out of range value was deemed clinically significant or not clinically significant will be indicated.

The observed results and change from baseline for all 12-lead ECG parameters will be summarized descriptively by treatment group and timepoint. Boxplots of the observed values

will also be provided. QTcF values that are > 450 msec and increase from baseline > 30 msec will be flagged in the data listing.

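### SAP 8.1 and 8.1.2 derive no change from baseline for postdose repeat, unscheduled and Early Termination readings, which contradicts 8.6.2 to 8.6.4 and stops the joint QTcF flag from firing on those ECGs

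*SAP*

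**What the plan says.** SAP 8.1.1 removes ET readings from the summary tables and gives a reason: "As Early Termination measurements are not associated with any scheduled timepoint, it will be excluded from all calculations of summary statistics". It removes postdose repeat and unscheduled readings from them as well.

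SAP 8.1.2 goes further: "Post dose repeats, unscheduled assessments, and ET measurements will be excluded from all calculations, with the exception of the baseline derivation". The reach of that sentence depends on what *all calculations* means, and SAP 8.1 says "this includes, but is not limited to, summary statistics, statistical analyses, baseline derivation, and changes from baseline".

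SAP 8.6.2, 8.6.3 and 8.6.4 say that every laboratory, vital-sign and ECG parameter will be listed with its change from baseline. SAP 8.6.4 adds a QTcF flag for values above 450 msec, joined by *and* to "increase from baseline > 30 msec will be flagged in the data listing".

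On how far the listings run, SAP 8.1 says they "include data up to the point of study completion or discontinuation".

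Protocol 4.6 has the site try to complete the final-day assessments when a subject withdraws. Protocol Appendix 4, footnote v, wants the ECG, vital-sign and laboratory results available for review before release. ET readings are therefore expected to exist.

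**The concern.** Keeping off-schedule readings out of by-timepoint tables is ordinary practice. Those readings are already out under 8.1.1, so for safety data the main further effect of 8.1.2 is in the listings: it removes the change value, and with it any flag that depends on change. No by-timepoint argument applies there. A programmer cannot follow both 8.1.2 and 8.6.2 to 8.6.4.

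Safety and tolerability is the secondary objective, and 8.6.4 names a QTcF rise as something to mark. Unscheduled and ET ECGs are among the readings where a reviewer would most want that mark. ET laboratory and ECG values can also be the only postdose values of their type for a subject who leaves early in a period, and no by-treatment summary of those parameters uses them.

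**Working it through.** **1. The rule chain.** 8.1 puts changes from baseline inside *all calculations*. 8.1.2 takes postdose repeat, unscheduled and ET readings out of *all calculations*, sparing only the baseline derivation. Those readings therefore have no derived change. 8.6.2 to 8.6.4 require a change for every listed parameter. The two instructions conflict.

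**2. The QTcF flag.** Read jointly, the flag fires when QTcF > 450 and QTcF − baseline > 30. Take a baseline of 420 and a postdose value of 465 msec (illustrative assumptions, not from the documents): 465 > 450, and 465 − 420 = 45 > 30.

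- Original scheduled ECG: both conditions can be evaluated, so it is flagged.
- Repeat, unscheduled or ET ECG: the change is not derived, the second condition cannot be met, so it is not flagged.
- With change derived for all readings: flagged in both cases.

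The result does not depend on the assumed values. Under the joint reading, no QTcF value on an excluded ECG can trigger the flag. If 8.6.4 meant two separate flags, the 450 msec part would still fire and the 30 msec part would not.

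**3. When a withdrawn subject has no scheduled postdose value.** Protocol Appendix 4 gives the times. Footnote e, for ECGs, includes "Day 8 (predose), Day 11 (ie, 72 hours after LOXO-305 dosing on Day 8", with no 2 h ECG on Day 8 or Day 18. Footnote p says that laboratory tests "will be performed at Screening, Check-in (Day -1), Days 4, 7, 11, 17, 21, and at EOT (Day 25) or ET". Footnote f gives vital signs from 2 h after each LOXO-305 dose. Each dose is followed by 168 h of PK sampling, so the share is the first scheduled time divided by 168.

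| First scheduled postdose value | Day 1 dose | Day 8 dose | Day 18 dose |
|---|---|---|---|
| ECG | 2 h (2/168 = 1.2%) | 72 h (72/168 = 42.9%) | 72 h (42.9%) |
| Vital signs | 2 h (1.2%) | 2 h (1.2%) | 2 h (1.2%) |
| Laboratory | 72 h (42.9%) | 72 h (42.9%) | 72 h (42.9%) |

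At the half-life of about 18 h in Protocol 1.3.2, which the protocol itself calls uncertain, 72/18 = 4 half-lives. A subject who leaves inside one of these windows adds no postdose value of that type to that treatment's summary, because the ET value is excluded.

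**4. What is untouched.** 8.1.2 keeps the original scheduled value in all postdose calculations, with no exception for subjects who later leave. To have no postdose ECG, vital-sign or laboratory value in any table, a subject would have to leave within about 2 h of the Day 1 dose or miss scheduled readings.

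**5. Where the listings end.** SAP 4 defines study completion as the last subject's follow-up call. SAP 8.1 generally judges a subject's completion at the end-of-treatment visit. For completers the cut-off is therefore ambiguous. For discontinued subjects, 8.1 stops at discontinuation. Yet SAP 4 has them called 7 ± 2 days after ET and still collects SAEs and drug-related AEs, and 8.6.1 says all AEs will be listed. Only there is the conflict direct.

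**The case against.** The strongest reply is that little is lost. SAP 8.1 lists all data in the database, so excluded readings are visible. The reference-range and clinical-significance flags need no baseline. Protocol 7.2.1 records as AEs any events noted on ECG, vital signs or laboratory tests, and SAP 8.6.1 tabulates TEAEs, including those leading to discontinuation. The summary exclusion has a stated reason, and Protocol 8.4 plans only descriptive summaries by timepoint. A programmer might let the specific promise in 8.6.4 override the general rule in 8.1.2, and the table and listing shells, not available here, may settle it.

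Most of this stands, and it rules out several stronger readings that a reader might infer:

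- *The flag can never fire for a subject withdrawn for safety.* Not supported: it works on that subject's scheduled ECGs.
- *Such a subject disappears from every summary.* Not supported: scheduled values and TEAEs are counted, and vital signs start at 2 h.
- *The exclusions make the safety tables look cleaner.* Not shown. For repeats the original value is kept, so an abnormal original stays in even if its repeat is normal. Protocol 7.2 allows repeats at discretion, so an excluded reading need not mean that something went wrong. The documents give no withdrawal rate.
- *The listing cut-off drops all follow-up data.* Not supported, given the definition of study completion in SAP 4.

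The reply does not remove the contradiction between 8.1.2 and 8.6.2 to 8.6.4. Leaving a programmer to choose which section prevails is what an SAP should avoid.

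**Conclusion.** The point holds as an internal contradiction with a limited practical effect. Taken literally, the SAP gives no change from baseline to postdose repeat, unscheduled and ET readings, so the joint QTcF flag fires on none of those ECGs. Early withdrawal also leaves a treatment's laboratory summary without that subject for the first 72 h after any LOXO-305 dose. For ECGs the window is 72 h after the Day 8 and Day 18 doses and 2 h after the Day 1 dose.

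This rests on reading *and* in 8.6.4 as a joint condition and on the current Appendix 4 footnotes. How many subjects it would affect cannot be estimated from the documents. The primary PK analysis is not involved. It is worth correcting before database lock because the correction costs almost nothing.

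**What to change.** Replace the exclusion in SAP 8.1.2 with wording such as:

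> Repeat, unscheduled and ET readings taken after dosing are left out of by-timepoint summary statistics only. In the listings, their change from baseline is derived against the applicable period baseline, and the QTcF flag is applied to them as to scheduled readings. Readings taken after the Day 15 dose and before the Day 18 dose are labelled omeprazole alone.

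The last sentence follows SAP Table 1 and the TEAE assignment in 8.6.1. Tying every reading to the last LOXO-305 dose would instead place omeprazole-only readings under Treatment A or B. SAP 8.1.3 defines baseline only around LOXO-305 doses, and its Treatment C values fall on Day 17 (laboratory) and Day 18. It should therefore say which reading serves as baseline for Days 15 to 17. A predose ECG and vital signs are scheduled on Day 15; the last laboratory panel before then is on Day 11.

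In 8.6.4, say whether the QTcF conditions are joint or separate. In 8.1, state that listings run through the follow-up call for all subjects, including those who discontinued.

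The cost is SAP wording and a small change to the dataset derivation. No new data are needed, and the by-timepoint tables stay as they are.

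Optionally, add a row per treatment for the maximum postdose QTcF change, including these readings. It gives slightly more weight to subjects with more readings, so it needs a footnote. A similar row for the worst laboratory value would first need a stated direction for each parameter, and this point does not depend on it.

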8.1.3. Definitions of Baseline and Change from Baseline

Baseline value is defined as the last non missing measurement before administration of LOXO-305 in each treatment period. In general, baseline refers to the pre-dose value collected on Day 1 Treatment A or B, Day 8 Treatment A or B, and Day 18 Treatment C. For laboratory tests, baseline is the value collected on Day -1 Treatment A or B, Day 7 Treatment A or B, and Day 17 Treatment C.. If the date/time of the value is incomplete or missing, it will be excluded from the baseline calculation, unless the incomplete date/time indicates the value was recorded prior to the last dose.

Individual changes from baseline will be calculated by subtracting the individual subject’s baseline value from the value at the timepoint. The mean change from baseline will be defined as the mean of the individual changes from baseline for all subjects.

See [Section 8.1.2](#) for more detail on handling repeat and unscheduled readings in the calculations.

8.2. Subject Disposition and Population Assignment

Subject disposition and population assignment will be listed.

A summary table by treatment sequence will be provided, based on the all subjects population.

8.3. Screening Demographics and Baseline Characteristics

The screening demographics and baseline characteristics including age, sex, race, ethnicity, height, body weight, and body mass index will be listed.

A summary table by treatment sequence will be provided, based on the safety population.

8.4. Prior and Concomitant Medication

Prior medication will be defined as medication that ends prior to the first dose. Concomitant medication will be defined as medication that starts during or after the first dose or starts but does not end prior to the first dose.

Prior and concomitant medications will be coded using the World Health Organization Drug Dictionary (WHODrug) Global, Format B3, Version September 2019. Prior and concomitant medications will be listed.

8.5. Pharmacokinetic Assessments

8.5.1. Pharmacokinetic Analysis

The following PK parameters will be determined where possible from the plasma concentrations of LOXO-305 using non-compartmental methods performed using Phoenix WinNonlin (Certara USA, Inc.) version 8.1 or higher:

Parameter	Definition
C_{\max}	maximum observed plasma concentration
t_{\max}	time to maximum observed concentration
AUC_{0-24}	area under the concentration-time curve (AUC) from Hour 0 to 24 hours postdose, calculated using the linear trapezoidal rule for increasing and decreasing concentrations
AUC_{0-t}	area under the concentration-time curve (AUC) from Hour 0 to the last measurable concentration, calculated using the linear trapezoidal rule for increasing and decreasing concentrations
$AUC_{0-\infty}$	AUC extrapolated to infinity, calculated using the formula: $AUC_{0-\infty} = AUC_{0-t} + \frac{C_t}{\lambda_z}$ where C_t is the last measurable concentration and λ_z is the apparent terminal elimination rate constant
$\%AUC_{\text{extrap}}$	percentage extrapolation for $AUC_{0-\infty}$
λ_z	apparent terminal elimination rate constant, where λ_z is the magnitude of the slope of the linear regression of the log concentration versus-time profile during the terminal phase
$t_{1/2}$	apparent terminal elimination half-life (whenever possible), where $t_{1/2} = \text{natural log (ln)}(2)/\lambda_z$
CL/F	apparent systemic clearance

Additional PK parameters may be determined where appropriate. The number of points used to estimate λ_z , the lower and upper points used in estimation, λ_z span ratio, and the adjusted coefficient for determination of exponential fit (R^2 adjusted) will be presented in a listing.

The PK analysis will, where possible, be carried out using actual postdose times recorded in the raw data. If actual times are missing, nominal times may be used with sponsor approval.

Concentrations are used as supplied by the analytical laboratory for PK analysis. The units of concentration and resulting PK parameters, with amount or concentration in the unit, will be presented as they are received from the analytical laboratory.

C_{max} and t_{max} will be obtained directly from the plasma concentration-time profiles. For multiple peaks, the highest postdose concentration will be reported as C_{max} . In the case that multiple peaks are of equal magnitude, the earliest t_{max} will be reported.

8.5.1.1. Criteria for Handling Concentrations Below the Limit of Quantification in Pharmacokinetic Analysis

Concentration values that are below the level of quantification (BLQ) will be set to zero, with defined exceptions as follows;

- Any embedded BLQ value (between 2 quantifiable concentrations) and BLQ values following the last quantifiable concentration in a profile will be set to missing for the purposes of PK analysis.
- If there are late positive concentration values following 2 BLQ concentration values in the apparent terminal phase, these values will be evaluated. If these values are considered to be anomalous, they will be set to missing.
- If an entire concentration-time profile is BLQ, the profile will be excluded from the PK analysis.
- If a predose concentration is missing, it may be set to zero in PK analysis by default within Phoenix WinNonlin.

8.5.1.2. Criteria for the Calculation of an Apparent Terminal Elimination Rate Constant and Half-Life

8.5.1.2.1. Number of Data Points

At least 3 data points will be included in the regression analysis and preferably should not include C_{max} .

